### 3.3.2.2 Efficacy

The clinical efficacy information summarized here includes data from the NSCLC and ovarian cancer expansion cohorts of the ongoing Phase I Trial EMR 100070-001, the 20 subjects in the gastric cancer expansion cohort of the ongoing Phase I Trial EMR 100070-002, and the 88 patients in the Phase II EMR 100070-003 Trial in Merkel Cell carcinoma.

The NSCLC expansion cohort in the ongoing Phase I Trial EMR 100070-001 had a cutoff date of 15 January 2015, 6 months after start of avelumab treatment of the last subject in this expansion cohort (a total of 184 treated subjects). The objective response rate (ORR) based on confirmed and unconfirmed responses for subjects treated in the NSCLC expansion cohort was 14.1% (26 of 184 NSCLC subjects). Progression free survival (PFS) and overall survival (OS) were all evaluated for all NSCLC subjects treated in the expansion phase. As of 15 January 2015, the median PFS and OS for the NSCLC treatment expansion cohort were 11.6 weeks and 8.4 months, respectively. A total of 142 out of the 184 subjects in the second-line NSCLC expansion cohort provided tumor samples that were evaluable for PD-L1 expression. Antitumour activity was seen in tumors defined as PD-L1+ and PD-L1- using prespecified PD-L1 expression levels on tumour cells (1%, 5%, and 25%) and tumour-

associated immune cells. In patients with PD-L1+ vs PD-L1- tumours, there was no significant difference in response rates or OS, whereas PFS was longer in those patients with PD-L1+ tumours compared with PD-L1- tumours in an analysis based on a 1% cut-off for tumour cell staining (hazard ratio for progressive disease, 0.45; 95% CI: 0.27, 0.75).

The ovarian cancer expansion cohort had a data cutoff of 23 October 2015. This cohort enrolled and treated a total of 124 subjects. The ORR based on confirmed and unconfirmed responses for subjects treated in the ovarian cancer expansion cohort was 9.7% (12 of 124 subjects). In 6 of the 12 responders (50.0%), the responses were ongoing at the time of the data cutoff. The median PFS for the ovarian cancer expansion cohort was 11.3 weeks (95% CI: 6.1 to 12.0 weeks).

The gastric cancer expansion cohort in the ongoing Phase I Trial EMR100070-002 had a data cut off of 11 March 2015 for 20 subjects being treated with 10 mg/kg of avelumab once every 2 weeks. As of the data cutoff, 3 of 20 subjects responded to study treatment (all responses were PRs and all responses were confirmed responses), and the BOR was 15.0% (95% CI: 3.2% to 37.9%). Two of the responders had the first response at around Week 6 and 1 responder had the first response at around Week 18. Two of the 3 responders had their response continued at the time of the data cutoff. The median PFS of this group according to RECIST 1.1 was 11.9 weeks (95% CI: 6.0 to 12.3 weeks). The Kaplan-Meier estimates predicted a PFS rate of 43.3% at 12 weeks.

The Phase II EMR 100070-003 Trial in Merkel Cell carcinoma gave avelumab to 88 patients and resulted in an objective response in 28 patients (31.8% [95.9% CI 21.9-43.1]), including 8 complete responses. Responses were ongoing in 23 (82%) of 29 at the time of data cut off 03 March 2016. Median PFS was 2.7 months (95% CI: 1.4, 6.9), and the proportion of subjects who were progression-free at 6 months was 40% (95% CI: 29, 50).

For further data, please refer to the current Investigator's Brochure for avelumab.

### 3.4 Purpose and Rationale

Data supporting PD-L1 inhibition in prostate cancer was found when enzalutamide resistant cell lines and xenografts on mice had increased PD-L1. Our own cell lines established at Duke that are enzalutamide resistant also demonstrate upregulation of PD-L1 at the protein and RNA level as compared with the parental cell lines, suggesting that PD-L1 is an adaptive response to stress and is highly dynamic (data unpublished). Further, we have also looked at a cohort of patients with NEPC/SCPC using a tissue microarray for PD-L1 expression by immunohistochemistry and have found that a small subset (~20% small cell, ~10% adenocarcinoma) of these cases express high levels of PD-L1 (data unpublished). Further still is evidence showing that there is a high burden of genetic mutations in NEPC which has been seen in other cancers to confer susceptibility to immunotherapy.

Given the emerging role of immunotherapy across multiple tumor types to produce durable responses, and given the similarity of small cell by both histology and its response to current chemotherapy, we hypothesize that avelumab will produce a clinical and radiographic response in NEPC that will be durable in a subset of patients. In this study, we are defining the NEPC "phenotype"

based on clinical poor risk features of AR-independence or based on histologic evidence of NEPC in tissue or serum.

## 4 OBJECTIVES AND ENDPOINTS

### 4.1 Primary Endpoint

To determine the efficacy of PD-L1 inhibition with avelumab as measured by a modified PCWG3, where RECIST 1.1 is replaced with iRECIST, a modified RECIST 1.1 for immune-based therapeutics, radiographic response rate in men with metastatic neuroendocrine-like prostate cancer.

### 4.2 Secondary Endpoints

1. To describe the efficacy of PD-L1 inhibition with avelumab as measured by PCWG3 using RECIST1.1
2. To describe the radiographic progression free survival (rPFS) of PD-L1 inhibition with avelumab using modified PCWG3 with both RECIST 1.1 and iRECIST criteria in this setting.
3. To describe the overall survival of PD-L1 inhibition in this setting.
4. To described the toxicities and safety of PD-L1 inhibition with avelumab in men with metastatic neuroendocrine-like prostate cancer.

### 4.3 Exploratory Endpoints

1. To describe the impact of PD-L1 inhibition with avelumab on blood-based biomarker changes over time, including PSA, chromogranin-A, cell free DNA, LDH, and alkaline phosphatase.
2. To determine if levels of circulating biomarkers secreted by neuroendocrine-like prostate cancers correlate with clinical and radiographic treatment response
3. To determine if the presence of different immunohistochemical markers on the pre-biopsy specimens prognosticates clinical and radiographic treatment response
4. To determine if the level of different circulating immune cells correlate with both progressive addition of immunotherapy as well as clinical and radiographic treatment response or disease progression
5. To determine if levels of cell free DNA correlate with clinical and radiographic treatment response
6. To isolate prostate neuroendocrine-like CTCs for ex vivo growth and culture and characterization studies.

## 5 INVESTIGATIONAL PLAN

### 5.1 Study Design

This is an open label, single arm, phase 2 study of men with neuroendocrine phenotype prostate cancer to assess the safety and efficacy of avelumab 10 mg/kg IV every 2 weeks until progression or intolerable side effects. Cycles will be 4 weeks long and thus include 2 doses of avelumab. This study will be at multiple centers with the Duke Cancer Institute as the lead site. For stage 1, Duke will serve as the single site for this study. For stage 2, the study would be expanded to include additional sites

through the Department of Defense Prostate Cancer Clinical Trials Consortium (DOD PCCTC). All subjects will be followed for disease progression and death from the date that the subjects were registered to the protocol.

At radiologic progression a standard of care post-treatment progression biopsy will be collected at the discretion of the treating provider, and if proper consent is obtained, additional tissue will be collected for research tests including assessments of resistance mechanisms and immune checkpoint status. The additional research tissue will be banked in the Biospecimen Repository & Processing Core (BRPC) under Pro00080869. The study team will also pursue dual consent to BRPC Pro00035974 for future unspecified research.

Men will continue on their ADT used at entry into study per investigator with subsequent changes made per investigator. Men not on ADT at time of entry due to being purely SCPC can remain off ADT. Men with SCPC on ADT at study entry can remain on ADT per investigator while all men with mixed histologies should remain on active ADT during trial participation.

Men will be allowed to receive palliative radiation to any disease site indicated by the treating physician at any time before or during the study, provided that another untreated site of measureable disease is present at baseline.

## 5.2 Drug Discontinuation Criteria

All subjects will be monitored for adverse events (AEs) on treatment using NCI CTCAE v4.0 or the most current version. Stopping rules based on unacceptable toxicities will be used in this study. Avelumab will be discontinued in the patient if there is unacceptable toxicity defined as:

- Any grade 5 treatment-related death
- Any Grade 4 AE except for single laboratory values out of normal range that are unlikely related to study treatment as assessed by the Investigator, do not have any clinical correlate, and resolve within 7 days with adequate medical management
- Any Grade 3 AE except for any of the following:
  - Transient ( $\leq 6$  hours) Grade 3 flu-like symptoms or fever, which is controlled with medical management
  - Transient ( $\leq 24$  hours) Grade 3 fatigue, local reactions, headache, nausea, emesis that resolves to Grade  $\leq 1$
  - Single laboratory values out of normal range (excluding Grade  $\geq 3$  liver function test increase) that are unlikely related to study treatment according to the Investigator, do not have any clinical correlate, and resolve to Grade  $\leq 1$  or baseline within 7 days or by the next visit with adequate medical management
  - Tumor flare phenomenon defined as local pain, irritation, or rash localized at sites of known or suspected tumor
  - Change in Karnofsky Performance Status to  $\leq 40$  that does not resolve to  $\geq 50$  within 14 days (infusions should not be given on the following cycle, if the Karnofsky Performance Status is  $\leq 40$  on the day of study drug administration)

Grade 2 immune-related AEs should be managed as follows:

- If a Grade 2 ADR resolves to Grade  $\leq 1$  by the last day of the current cycle, treatment may continue.

- If a Grade 2 ADR does not resolve to Grade  $\leq 1$  by the last day of the current cycle, infusions should not be given on the following cycle. If at the end of the following cycle the event has not resolved to Grade 1, the subject should permanently discontinue treatment with avelumab ADR (except for hormone insufficiencies and conditions that are adequately treated with medical management, that can be managed by replacement therapy; for these hormone insufficiencies, up to 2 subsequent doses may be omitted). Patients with transient, minor Grade 2 ADRs, may be permitted to continue therapy with permission of the study PI provided the patient is adequately managed medically.
- Upon the second occurrence of the same Grade 2 ADR (except for hormone insufficiencies that can be managed by replacement therapy) in the same subject, treatment with avelumab has to be permanently discontinued

There will be no dose modifications for avelumab in this study. Dose interruptions for reasons other than toxicity (e.g., surgical procedures) may be allowed with PI approval. The investigator and the PI will determine the acceptable length of treatment interruption. If avelumab is withheld for > 8 weeks then study treatment will be permanently discontinued.

If the investigator believes the patient is likely to derive clinical benefit, avelumab treatment can be resumed after being withheld for > 8 weeks. If a patient must be tapered off corticosteroids used to treat adverse events, study treatment may be withheld for > 8 weeks with PI approval.

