## 5.5 Management of Immune-mediated Adverse Reactions

Please see the table below for management of immune-mediated adverse reactions

Since inhibition of PD-L1 stimulates the immune system, immune-related AEs (irAEs) may occur. Treatment of irAEs is mainly dependent upon severity (NCI-CTCAE grade):                  Grade 1 to 2: treat symptomatically or with moderate dose steroids, more frequent monitoring                  Grade 1 to 2 (persistent): manage similar to high grade AE (Grade 3 to 4)                  Grade 3 to 4: treat with high dose corticosteroids                  Treatment of gastrointestinal, dermatological, pulmonary, hepatic and endocrine irAEs should follow guidelines set forth in the table below.
		

Gastrointestinal irAEs
		

Severity of Diarrhea / Colitis (NCI-CTCAE v4.03)
	
Management
	
Follow-up

Grade 1 Diarrhea: < 4 stools/day over Baseline Colitis: asymptomatic
	
Continue avelumab therapy Symptomatic treatment (for example, loperamide)
	
Close monitoring for worsening symptoms Educate subject to report worsening immediately If worsens: Treat as Grade 2 or 3/4

Grade 2 Diarrhea: 4 to 6 stools per day over Baseline; IV fluids indicated < 24 hours; not interfering with ADL Colitis: abdominal pain; blood in stool
	
Delay avelumab therapy Symptomatic treatment
	
If improves to Grade 1: Resume avelumab therapy If persists > 5 to 7 days or recur: 0.5 to 1.0 mg/kg/day methylprednisolone or equivalent When symptoms improve to Grade 1, taper steroids over at least 1 month, consider prophylactic antibiotics for opportunistic infections, and resume avelumab therapy per protocol (if reduced to 10 mg/day or less of prednisone equivalent). If worsens or persists > 3 to 5 days with oral steroids: Treat as Grade 3 to 4

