
Grade 3 to 4 Diarrhea (Grade 3): ≥ 7 stools per day over Baseline; incontinence; IV fluids ≥ 24 hrs.; interfering with ADL Colitis (Grade 3): severe abdominal pain, medical intervention indicated, peritoneal signs Grade 4: life-threatening, perforation
	
Discontinue avelumab therapy per protocol 1.0 to 2.0 mg/kg/day methylprednisolone IV or equivalent Add prophylactic antibiotics for opportunistic infections Consider lower endoscopy
	
If improves: Continue steroids until Grade 1, then taper over at least 1 month If persists > 3 to 5 days, or recurs after improvement: Add infliximab 5 mg/kg (if no contraindication), Note: Infliximab should not be used in cases of perforation or sepsis

Dermatological irAEs
		

Grade of Rash (NCI-CTCAE v4)
	
Management
	
Follow-up

Grade 1 to 2 Covering ≤ 30% body surface area
	
Symptomatic therapy (for example, antihistamines, topical steroids) Continue avelumab therapy
	
If persists > 1 to 2 weeks or recurs: Consider skin biopsy Delay avelumab therapy Consider 0.5 to 1.0 mg/kg/day methylprednisolone IV or oral equivalent. Once improving, taper steroids over at least 1 month, consider prophylactic antibiotics for opportunistic infections, and resume avelumab therapy once patient has reached prednisone equivalent of 10 mg/d and improving. If worsens: Treat as Grade 3 to 4

Grade 3 to 4 Covering > 30% body surface area; life threatening consequences
	
Delay or discontinue avelumab therapy Consider skin biopsy Dermatology consult 1.0 to 2.0 mg/kg/day methylprednisolone IV or IV equivalent
	
If improves to Grade 1: Taper steroids over at least 1 month and add prophylactic antibiotics for opportunistic infections Resume avelumab therapy

Pulmonary irAEs
		

Grade of Pneumonitis (NCI-CTCAE v4)
	
Management
	
Follow-up

Grade 1 Radiographic changes only
	
Consider delay of avelumab therapy Monitor for symptoms every 2 to 3 days Consider Pulmonary and Infectious Disease consults
	
Re-image at least every 3 weeks If worsens: Treat as Grade 2 or Grade 3 to 4

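### The Grade 3 to 4 rash row in 5.5 lets avelumab be delayed and resumed where 5.2 requires it to be stopped, and nothing says which section governs

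*Combined protocol and SAP*

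**What the plan says.** **Section 5.2 (Drug Discontinuation Criteria)** states a rule: "Avelumab will be discontinued in the patient if there is unacceptable toxicity defined as" a list of events. Two items matter here.

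- Grade 4: "Any Grade 4 AE except for single laboratory values out of normal range that are unlikely related to study treatment", with further conditions on those laboratory values. There is no other Grade 4 exception.
- Grade 3: any event outside an enumerated list. The only rash on the list is "Tumor flare phenomenon defined as local pain, irritation, or rash localized at sites of known or suspected tumor". Local reactions are also listed, but only if they last 24 hours or less.

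For Grade 2 immune-related events, 5.2 allows treatment to continue or be held. If the same Grade 2 reaction happens again "in the same subject, treatment with avelumab has to be permanently discontinued", unless it is a hormone insufficiency managed by replacement.

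**Section 8.5 (End of Treatment)** says that study treatment stops on unacceptable toxicity.

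**Section 5.5 (Management of Immune-mediated Adverse Reactions)** opens with "Treatment of gastrointestinal, dermatological, pulmonary, hepatic and endocrine irAEs should follow guidelines set forth in the table below". Its Grade 3 to 4 rash row covers more than 30% "body surface area; life threatening consequences". The management cell begins "Delay or discontinue avelumab therapy Consider skin biopsy Dermatology consult". The follow-up cell says that, on improvement to Grade 1, steroids are tapered over at least a month and avelumab is resumed. The row does not separate Grade 3 from Grade 4.

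**The concern.** One event draws two different instructions. Under 5.2, a Grade 3 or Grade 4 generalized rash ends avelumab. Under the 5.5 row, the same rash may lead to a pause and then more avelumab. A treating physician managing a rash will probably open the rash table, and that table expressly offers the option that 5.2 rules out.

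What is at stake is the safety of the individual patient: re-exposure to a checkpoint inhibitor after a severe, possibly life-threatening, immune reaction. Stage 1 runs at one site, but investigators there can already read the sections differently. Section 11.9 foresees 2 to 3 additional sites for stage 2, which gives more room for readings to diverge.

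**Working it through.** No arithmetic applies, so the check is a side-by-side reading.

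**Step 1: is generalized Grade 3 or 4 rash exempt under 5.2?** At Grade 4 only laboratory values are exempt, so rash is not. At Grade 3 the nearest entries are tumor flare, which is confined to tumor sites, and local reactions of 24 hours or less. Neither describes rash over more than 30% of the body surface. Result: 5.2 requires discontinuation at both grades.

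**Step 2: what does 5.5 allow in its rows labelled Grade 3 to 4?**

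| 5.5 row, Grade 3 to 4 | Avelumab | Resumption given? | Agrees with 5.2? |
|---|---|---|---|
| Diarrhea/colitis | Discontinue, per protocol | No | Yes |
| Rash | Delay or discontinue | Yes, at Grade 1 | Only if discontinue is chosen |
| Pneumonitis | Discontinue | No | Yes |
| Liver tests | Discontinue | No | Yes |

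Three of the four rows agree with 5.2. Rash is the exception, and it is so for Grade 4 as well as Grade 3.

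**Step 3: does any sentence settle precedence?** The 5.5 lead-in sends dermatological events to the table but does not mention 5.2. Section 5.2 does not mention the table. Section 8.5 supports stopping but does not refer to 5.5. No precedence sentence was found in 5.2 to 5.5, 8.5 or 8.8.

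**Step 4: does the 8-week hold limit in 5.2 close the gap?** No. It limits the length of a hold and does not say whether a hold is allowed. It is also not firm: 5.2 lets treatment resume after a longer hold if the investigator expects benefit. It adds "If a patient must be tapered off corticosteroids used to treat adverse events, study treatment may be withheld for" more than 8 weeks with PI approval.

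**Step 5: the Grade 2 rows.** The Grade 1 to 2 rash row says that if rash recurs, avelumab is delayed, steroids are considered and tapered, and avelumab is then resumed. If the recurrent rash is Grade 2, this conflicts with the second-occurrence rule in 5.2. If it is Grade 1, there is no conflict. The Grade 2 diarrhea/colitis row has the same structure (recurrence, steroids, resumption) but makes resumption subject to the protocol, which can be read as deferring to 5.2. The Grade 2 pneumonitis and liver-test rows do not mention recurrence.

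**The case against.** The best defence is that the two sections can be reconciled. Discontinuing is one of the rash row's own options, so a site that chooses it satisfies both. Section 5.2 is worded as a requirement and 5.5 as guidance, and 8.5 sides with 5.2. The two diarrhea/colitis rows that refer back to the protocol suggest that the table was meant to defer. Other safeguards exist too: a life-threatening rash is a serious event reportable within 24 hours (9.2, 9.3), the PI reviews adverse events continuously (10.1) and may withdraw a subject (8.8.1), and a treatment-related Grade 3 or higher event counts toward the stopping rule in 5.3 whether or not drug is resumed.

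Part of this stands. A careful reader may well conclude that 5.2 governs, and the safeguards make unnoticed re-dosing less likely. But the rash row has no cross-reference of its own, it offers delay as an equal alternative, and it prints the instruction to resume. None of the safeguards tells the physician which instruction to follow.

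A reader might infer more than the text supports:

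- *That 5.5 as a whole relaxes 5.2.* It does not. Three of its four Grade 3 to 4 rows match 5.2.
- *That every recurrent rash creates a conflict.* Only a recurrent Grade 2 rash does. Section 5.2 also lets men with transient, minor Grade 2 reactions continue with PI permission, and how that relates to recurrence is open to argument.
- *That the endocrine and suspected-myocarditis rows contradict 5.2 outright.* They carry no grades, so they conflict only when the event reaches a grade at which 5.2 requires a stop.

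**Conclusion.** The inconsistency is real and centres on the rash rows. As written, a site can follow the Grade 3 to 4 rash row and re-dose a man whom 5.2 requires to stop, including after life-threatening rash. The secondary conflict concerns a second Grade 2 rash. The Grade 2 diarrhea/colitis row carries the same ambiguity in weaker form.

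The conclusion rests on two readings: that the Grade 3 exception list in 5.2 is complete as printed, and that generalized rash falls under none of its entries. The number of men affected cannot be derived, because the documents give no expected rate of severe or recurrent rash. A reader might also infer an effect on the response-rate test, but none is claimed. The two-stage design, its error rates and the sample size do not depend on this wording. It deserves correction as a patient-safety instruction and does not threaten the trial's primary conclusion.

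**What to change.** 1. **Grade 4 rash.** Split the Grade 3 to 4 rash row in 5.5 so that the Grade 4 part reads *Permanently discontinue avelumab*.
2. **Grade 3 rash.** Choose one. Either remove the delay option and the resumption instruction from the row or, if the sponsor intends resumption, add Grade 3 rash that resolves to Grade 1 or less as a named exception in 5.2.
3. **Recurrent Grade 2 events.** In the Grade 1 to 2 rash row and the Grade 2 diarrhea/colitis row, add: *a second occurrence of the same Grade 2 event: permanently discontinue per 5.2*.
4. **Endocrine and suspected-myocarditis rows.** Leave these for the sponsor to align with 5.2 by named exception where resumption is intended. A general sentence making 5.2 override every row would be shorter. But it would also bar a restart after a Grade 3 suspected myocarditis whose immune cause has been ruled out, and that is a clinical choice for the sponsor.

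The cost is a wording amendment to 5.5 and, depending on the choices in items 2 and 4, named exceptions in 5.2. It needs no new data. The downside is that some men who recover from a Grade 3 or 4 rash, or from a recurrent Grade 2 event, lose the option to resume. How many cannot be derived from the documents.

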
Grade 2 Mild to moderate new symptoms
	
Delay avelumab therapy Pulmonary and Infectious Disease consults Monitor symptoms daily, consider hospitalization 1.0 mg/kg/day methyl-prednisolone IV or oral equivalent Consider bronchoscopy, lung biopsy
	
Re-image every 1 to 3 days If improves: When symptoms return to near Baseline, taper steroids over at least 1 month and then resume avelumab therapy and consider prophylactic antibiotics If not improving after 2 weeks or worsening: Treat as Grade 3 to 4

Grade 3 to 4 Severe new symptoms; New / worsening hypoxia; life-threatening
	
Discontinue avelumab therapy Hospitalize Pulmonary and Infectious Disease consults 2 to 4 mg/kg/day methylprednisolone IV or IV equivalent Add prophylactic antibiotics for opportunistic infections Consider bronchoscopy, lung biopsy
	
If improves to Baseline: Taper steroids over at least 6 weeks If not improving after 48 hours or worsening: Add additional immunosuppression (for example, infliximab, cyclophosphamide, IV immunoglobulin, or mycophenolate mofetil)

Hepatic irAEs (reportable per section 9.3)
		

Grade of Liver Test Elevation (NCI-CTCAE v4)
	
Management
	
Follow-up

Grade 1 Grade 1 AST or ALT > ULN to 3.0 x ULN and / or total bilirubin > ULN to 1.5 x ULN
	
Continue avelumab therapy
	
Continue liver function monitoring If worsens: Treat as Grade 2 or 3 to 4

Grade 2 AST or ALT > 3.0 to ≤ 5 x ULN and / or total bilirubin > 1.5 to ≤ 3 x ULN
	
Delay avelumab therapy Increase frequency of monitoring to every 3 days
	
If returns to Baseline: Resume routine monitoring, resume avelumab therapy If elevations persist > 5 to 7 days or worsen:

	Report per section 9.3	0.5 to 1 mg/kg/day methylprednisolone or oral equivalent and when LFT returns to Grade 1 or Baseline, taper steroids over at least 1 month, consider prophylactic antibiotics for opportunistic infections, and resume avelumab therapy

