Grade 3 to 4 AST or ALT > 5 x ULN and / or total bilirubin > 3 x ULN	Discontinue avelumab therapy Increase frequency of monitoring to every 1 to 2 days 1.0 to 2.0 mg/kg/day methylprednisolone IV or IV equivalent Add prophylactic antibiotics for opportunistic infections Consult gastroenterologist Consider obtaining MRI/CT scan of liver and liver biopsy if clinically warranted Report per section 9.3	If returns to Grade 2: Taper steroids over at least 1 month If does not improve in > 3 to 5 days, worsens or rebounds: Add mycophenolate mofetil 1 gram (g) twice daily If no response within an additional 3 to 5 days, consider other immunosuppressants per local guidelines
Endocrine irAEs		
Endocrine Disorder	Management	Follow-up
Asymptomatic TSH abnormality	Continue avelumab therapy If TSH < 0.5 x LLN, or TSH > 2 x ULN, or consistently out of range in 2 subsequent measurements: include T4 at subsequent cycles as clinically indicated; consider endocrinology consult	
Symptomatic endocrinopathy	Evaluate endocrine function Consider pituitary scan Symptomatic with abnormal lab / pituitary scan:	If improves (with or without hormone replacement): Taper steroids over at least 1 month and consider prophylactic antibiotics for opportunistic infections Resume avelumab therapy

	
Delay avelumab therapy 1 to 2 mg/kg/day methylprednisolone IV or by mouth equivalent Initiate appropriate hormone therapy No abnormal lab / pituitary MRI scan but symptoms persist: Repeat labs in 1 to 3 weeks / MRI in 1 month
	
Subjects with adrenal insufficiency may need to continue steroids with mineralocorticoid component

Suspicion of adrenal crisis (for example, severe dehydration, hypotension, shock out of proportion to current illness)
	
Delay or discontinue avelumab therapy Rule out sepsis Stress dose of IV steroids with mineralocorticoid activity IV fluids Consult endocrinologist If adrenal crisis ruled out, then treat as above for symptomatic endocrinopathy
	

Cardiac irAEs
		

Myocarditis
	
Management
	
Follow-up

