## **8.8 Early Withdrawal of Subjects(s)**

### **8.8.1 Criteria for Early Withdrawal**

Subjects may voluntarily withdraw from the study at any time. The PI may also withdraw a subject from the study at any time based on his/her discretion.

Reasons for PI-initiated withdrawal may include the following:

- Symptomatic disease progression or objective radiologic progression that is not consistent with iRECIST
- Unacceptable toxicity, intercurrent illness, or changes in the patient's condition (at the discretion of the treating physician) — Reason(s) for removal must be clearly documented in the physician progress note
- The patient may withdraw from study treatment at any time for any reason and still be followed per protocol.
- Provider decision that the subject is no longer clinically benefiting from avelumab

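### Section 5.2 makes an isolated, unrelated, quickly resolving liver-test rise a mandatory stop at Grade 3 but not at Grade 4

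*Combined protocol and SAP*

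**What the plan says.** Section 5.2 is a mandatory rule for the individual patient: "Avelumab will be discontinued in the patient if there is unacceptable toxicity defined as" the events it then lists. Two of its bullets matter here.

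- **Grade 4.** The trigger is "Any Grade 4 AE except for single laboratory values out of normal range that are unlikely related to study treatment". To be excused, the value must also lack a clinical correlate and resolve within 7 days. Liver tests are not mentioned.
- **Grade 3.** Any Grade 3 event is a trigger unless it fits a listed exception. The laboratory exception is worded much like the Grade 4 one, but a parenthesis removes liver-test rises of Grade 3 or higher from it: "liver function test increase) that are unlikely related to study treatment according to the Investigator".

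Section 5.5 covers related ground. Its introduction says that "hepatic and endocrine irAEs should follow guidelines set forth in the table below", which ties the table to immune-related events. The hepatic block, however, is organised by "Grade of Liver Test Elevation (NCI-CTCAE v4"). Its Grade 3 to 4 row is triggered by "AST or ALT > 5 x ULN and / or total bilirubin > 3 x ULN" and the action is "Discontinue avelumab therapy Increase frequency of monitoring to every 1 to 2 days".

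Section 8.8.1 separately allows the PI to withdraw a man, for reasons that include "Unacceptable toxicity, intercurrent illness, or changes in" his condition.

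**The concern.** A stopping rule should be at least as strict for the more severe event. In 5.2 the order is reversed for one kind of event: the milder liver-test rise compels discontinuation, and the more severe one is left to judgement.

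What is at stake is patient safety and consistent conduct. Liver-test rises put down to something other than avelumab are foreseeable in this population. Liver metastases are one of the qualifying poor-risk features, and men who have them may enter with AST or ALT up to 5 x ULN, which is the edge of the Grade 3 to 4 threshold in 5.5. If stage 2 opens, several sites would apply the rule and could handle the same laboratory result differently.

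**Working it through.** No calculation in the plan bears on this, so the check is to apply 5.2 as written to one case at each grade, and then see whether another section closes the gap.

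**Test case.** A single AST, ALT or bilirubin value, recorded as an adverse event, judged unlikely related to treatment, without clinical correlate, back to baseline within 7 days.

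| Condition in 5.2 | Grade 3 laboratory exception | Grade 4 laboratory exception |
|---|---|---|
| Single value out of range | required; met | required; met |
| Judged unlikely related | required; met | required; met |
| No clinical correlate | required; met | required; met |
| Resolution | to Grade 1 or below, or baseline, by 7 days or the next visit; met | within 7 days, level not stated; met |
| Liver tests removed from the exception | **yes** | **no** |
| Outcome | exception unavailable | exception available |

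**Grade 3.** The other exceptions (brief flu-like symptoms or fever; brief fatigue, local reaction, headache, nausea or vomiting; tumour flare; the performance-status item) do not fit a laboratory value. Discontinuation is required.

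**Grade 4.** Every condition of the exception is met. Section 5.2 does not require discontinuation.

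**Does the Grade 3 parenthesis carry over?** It refers to Grade 3 and above, which points to an intention to cover Grade 4. But it sits inside an exception to the Grade 3 rule and does not modify the separate Grade 4 bullet.

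**Does 5.5 settle it?** Its hepatic row can be read in two ways.

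1. The section title and introduction limit the table to immune-related events. The row then does not reach a value judged unrelated, and the reversal in 5.2 stands.
2. The row is driven by laboratory values alone, with no attribution test. It then orders discontinuation at both grades, and the Grade 4 bullet in 5.2 excuses a value for which 5.5 says stop.

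**Knock-on effects.**

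- The accrual rule in 5.3 counts treatment-related events of Grade 3 or higher, so a value judged unrelated does not enter it.
- Section 5.10 keeps every man who received a dose in the primary analysis, so the response-rate denominator does not change.
- One affected man as a share of the cohort: 1/18 = 5.6% in stage 1; 1/49 = 2.0% of the overall target.

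**The case against.** The strongest reply is that the protocol, read as a whole, already handles this. Section 5.2 sets a minimum, so an exception to one trigger is not permission to continue. If the hepatic row in 5.5 applies to any liver-test rise, it adds a stricter requirement, and a site can satisfy both sections by stopping. The PI can also withdraw the man under 8.8.1, and potential Hy's Law cases are reported as serious events under 9.3. On this view the fault is a misplaced phrase with no shown consequence.

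Part of this stands. Under the second reading of 5.5 the two sections can both be obeyed, the intention is fairly clear, and the exception does not itself keep anyone on drug. But that reading is not secure, because 5.5 is framed for immune-related events and the exception in 5.2 concerns only values judged unrelated. Even if it is right, a site that consults 5.2 alone is told that the Grade 4 value is excused. Discretion under 8.8.1 does not put a mandatory rule back in order.

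Three narrower points:

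- Section 9.1 makes a laboratory abnormality an adverse event only under certain conditions, so not every Grade 3 rise triggers 5.2. That filter applies equally at Grade 4 and leaves the reversal in place.
- The Grade 4 exception lacks the alternative of resolution by the next visit, so in timing it is the tighter of the two. This narrows the case but does not help once the value has resolved within 7 days.
- A value that reaches Grade 4 has also passed the Grade 3 threshold, so a site might apply the Grade 3 rule. Section 5.2 does not say to do so, and an event is usually graded at its worst.

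**Conclusion.** The rule is wrong as written and should be corrected. For a single liver-test rise that is judged unlikely related, has no clinical correlate and resolves within 7 days, 5.2 compels discontinuation at Grade 3 and not at Grade 4.

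The conclusion rests on reading the Grade 4 bullet literally and on the value being recorded as an adverse event. It does not depend on any assumed event rate: the documents give none, and the single-man shares above only show scale. The problem is narrow. It concerns a patient-level safety rule and has no bearing on the two-stage design or its error rates.

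**What to change.** In the Grade 4 bullet of 5.2, directly after the reference to single out-of-range laboratory values, insert *(excluding liver function test increase)*. Grade 4 liver-test rises then require discontinuation, as Grade 3 rises already do and in line with the joint Grade 3 to 4 hepatic row in 5.5.

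The cost is five words in one bullet at the next amendment, with no added visits, tests or patients. The clinical downside is that a rare man with a transient, unrelated Grade 4 rise, for example one driven by liver metastases, must stop avelumab.

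Dropping the liver exclusion from the Grade 3 exception would also restore the order, but it would loosen the rule and run against both the Grade 3-or-higher wording in 5.2 and the hepatic row in 5.5.
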